**Table 3 Summary of endpoints, intercurrent event strategy, and population level summaries for the exploratory objectives**

Endpoint	Intercurrent event strategy	Population level summary
S-K of 4.0-5.0 mmol/L (yes/no) after the LIDI at the 12-month visit	Observations included in analysis regardless of treatment discontinuation and additional therapy (treatment policy)	Odds Ratio (SZC/placebo)
Time to first occurrence of SCD, stroke, or hospitalization/intervention/ED visit due to arrhythmias (AF, bradycardia, asystole, VT [such as VF, VT, etc.]), or use of rescue therapy	Observations included in analysis regardless of treatment discontinuation and additional therapy (treatment policy).  Patients censored at the earliest of non-SCD, WoC, LTFU, other reasons of discontinuation and SED.	Hazard Ratio (SZC/placebo)
Number of events of rescue therapy use for hyperkalemia	Observations included in analysis regardless of treatment discontinuation and additional therapy (treatment policy).  Patients censored at the earliest of death, WoC, LTFU, other reasons of discontinuation or SED.	Rate ratio (SZC/placebo)

## 4.2.1 Primary Endpoint

### 4.2.1.1 Definition

The primary endpoint is the composite endpoint of time to first occurrence of adjudicated events of SCD, stroke, or hospitalization/ intervention/ ED visit due to arrhythmias (AF, bradycardia, asystole, ventricular tachyarrhythmia [VT, VF etc.]). The potential components of the primary endpoint will be individually adjudicated by an independent committee. Only events that are positively adjudicated will be used in deriving the primary composite endpoint and the individual components.

### 4.2.1.2 Derivations

**Censoring:** See Table 1 for the censoring rules for the different analyses.

**Time to event or censoring:** See Section 3.3.1.5 for the definition of the study day.

### 4.2.1.3 Handling of Dropouts and Missing Data

The missing data in the context of the main analysis of the primary objective are potential events that might have occurred after subjects have been prematurely censored (i.e. due to causes other than SED). Since the time-to-event analysis using the Cox regression depends on the assumption of noninformative censoring, corresponding to the missing-at-random

missing data pattern, sensitivity analyses will be performed to assess the robustness of the results with regards to this assumption. Explicitly, in case of a statistically significant result, a ‘tipping point’ analysis, where the risk of censored subjects in the SXC group experiencing an event post-censoring is increased until the statistical significance is lost, will be performed. Appendix 2 provides the technical details of the tipping point analysis.

The missing data will also be described in terms of the number and percentage of subjects in the respective treatment arm that do not experience a primary endpoint event and that are censored before the SED, as well as reasons for censoring.

#### **4.2.1.4 Main Analysis of the Primary Endpoint**

The analysis of the primary composite endpoint will be based on a Cox regression model that includes the following factors/covariates: treatment group, geographic region. The Efron method for handling ties will be used.

The estimate of the HR corresponding to the difference between treatment arms, the corresponding 95% two-sided confidence interval (CI) as well as the two-sided p-value for the null hypothesis of no difference will be reported. If the p-value falls below the significance limit as specified in Section 4.2.3, the null hypothesis will be rejected.

The contribution of each component of the primary composite endpoint to the overall treatment effect will be assessed. In the analysis of the components, all first events of the given type will be included, irrespective of any preceding non-fatal component of a different type. Each component in the composite endpoint will be analysed similarly to the composite primary endpoint, i.e. by means of a Cox regression.

Kaplan-Meier estimates will be calculated and plotted, both for the composite endpoint and for individual components. The KM estimate at 12, 24 and 36 months will be included in the tabular presentation of the primary endpoint analysis.

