### 2.2 Background

With the progression of CKD to ESRD the ability of the kidneys to eliminate potassium is eventually lost resulting in the need for renal replacement therapy to maintain a normal S-K. While kidney transplantation is the preferred treatment option for most patients with ESRD, dialysis remains the global standard of care for those awaiting, or not being eligible for, transplantation. Hemodialysis is the most common modality and is usually performed 3 times a week, with a Kd of 2.0 to 2.5 mmol/L being the most commonly used prescription (Karaboyas et al 2017). However, despite dialysis, hyperkalemia remains common in this population (62.9 per 100 patient-months at the end of the LIDI) (Yusuf et al 2016). These patients are therefore chronically exposed to the pro-arrhythmic effects of potassium, and at higher risk of SCD, which accounts for 26% of all deaths in the ESRD population (Jadoul et al 2012). Recent studies have shown that S-K levels above 5.6 mmol/L are associated with increased CV and all-cause mortality (Kovesdy et al 2007, Yusuf et al 2016).

Further, cardiac conduction disorders and arrhythmias are common in hemodialysis patients. The reported annualized event rate for arrhythmias requiring hospitalization is 13.6 per 100 person-years with 25.9% of hemodialysis patients having an admission for an arrhythmia event during a follow-up period of 2.2 years (Foley et al 2011).

Atrial fibrillation is one of the strongest risk factors for ischemic stroke and an independent predictor of death in the general population (Benjamin et al 1998, Dries et al 1998, Sankaranarayanan et al 2015, Wolf et al 1998). The estimated prevalence of AF among patients with ESRD in observational studies has been reported to be as high as 27% (Genovesi et al 2005, Soliman et al 2010). Rates of hospitalized stroke are reportedly 5- to 10-fold higher in dialysis patients when compared to non-ESRD patients, with ischemic strokes being the most common (Seliger et al 2003, Sozio et al 2009).

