##### **9.4.2.1 Primary Endpoint(s)**

The primary endpoint is time to the first occurrence of SCD, stroke, or hospitalization/intervention/ED visit due to arrhythmias (AF, bradycardia, asystole, ventricular tachyarrhythmia [such as VF, VT, etc]). In accordance with the ITT principle, participants will be censored at the common SED or at the time of withdrawal of informed consent.

Although numerous intercurrent events, including, eg, termination of study intervention or initiation of an additional treatment that potentially affects the primary outcome, exist in this

setting, the analysis will follow “Treatment Policy Strategy” (ICH E9(R1) 2020). That is, the occurrence of such intercurrent events will be ignored. The only exception to this rule is death not adjudicated as SCD: participants will be censored at that time point.

The primary hypothesis of no difference between study intervention arms will be evaluated by means of a Cox regression, with time to first event/censoring as response and study intervention arm and geographic region as covariates. Other covariates may also be included as appropriate; further details of the statistical model will be specified in the SAP. The HR estimate, its standard deviation, 95% confidence interval, and p-value will be provided. Kaplan-Meier estimates of time to the first occurrence of any event in the composite endpoint will be calculated and plotted.

The homogeneity of effect with regards to subgroups (eg, gender, age-groups, etc) will be examined as specified in the SAP.

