## **3 DATA ANALYSIS CONSIDERATIONS**

### **3.1 Timing of Analyses**

The study involves two interim analyses (the first interim analysis is for futility and the second interim analysis is for efficacy) and the final analysis.

Thus, there are three timepoints for planned analyses in the study: one corresponding to study completion, planned to take place when 730 subjects had an adjudicated primary composite event, and the other two corresponding to interim analyses planned to take place when 292 (40% information fraction) and 511 (70% information fraction) subjects, respectively had an adjudicated primary composite event. The interim analyses will be conducted by independent data monitoring committee (DMC) and will mainly be aimed at evaluating the primary objective of the study with the possibility of early stopping for either futility (at n=292 events) and for efficacy (at n=511 events). In case of an early stopping of the study at efficacy interim analyses, all analyses as specified in this document will be conducted. However, if the study stops for futility, only selected analyses covering key efficacy and safety outcomes will be conducted.

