### **3.3 Sample Size Determination**

The study is event-driven. The primary objective of the study is to evaluate the efficacy of SZC versus placebo in reducing the incidence of the primary composite endpoint.

Assuming the true HR for SZC versus placebo is 0.8, 730 primary endpoint events will result in 84.7% statistical power to demonstrate a statistically significant difference at either second interim analysis using two-sided significance level of 1.64% or at the final analysis using two-sided significance level of 4.46%. Based on an assumption that the event rate of the primary composite endpoint is approximately 0.11 per patient-year in the placebo group, it is expected that approximately 2800 participants will need to be randomized. The anticipated recruitment period is planned to be 32 months. The anticipated average treatment period is approximately 37 months, which in practice will be dependent on the actual event rate observed during the study, as the study duration is event driven. Any decision to increase or decrease participant numbers will be based on blinded event rate data (e.g., observed overall event rate), and study discontinuation rate.

Assuming a screen failure rate of 50%, approximately 5600 participants will be enrolled to achieve approximately 2800 participants randomly assigned (1:1) to study intervention (SZC or placebo).

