#### 4.2.1.7 Subgroup Analyses

The consistency of the treatment effect observed in the main analysis will be evaluated with respect to the following demographic/baseline characteristic and prognostic factors:

- Sex
- Age at baseline
  - categorization 1 (<65, 65 - 84, ≥ 85)
  - categorization 2 (<65, 65 - 74, ≥ 75)
  - categorization 3 (<65, ≥65)
- Race (White, Black or African American, Asian, American Indian or Alaska Native, Native Hawaiian or other Pacific Islander, Other, Not reported)
- Geographic Region (Asia, Europe, North America, South America)
- Region (USA, Non-USA)
- Baseline S-K (<5.5, 5.5-6.5, >6.5)
- BMI (<30, ≥ 30 kg/m^2)
- Ethnicity (Hispanic or Latino, Not Hispanic or Latino)
- Haemodialysis access type (Arteriovenous Fistula, Arteriovenous Graft, Tunnelled Catheter, Other)

- Historical arrhythmia (yes/no) at baseline.
- Prior History of
  - Atrial Fibrillation (Yes, No)
  - Ventricular Tachycardia (Yes, No)
  - Ventricular Fibrillation (Yes, No)
  - Stroke/TIA (Yes, No)

The Cox proportional hazards model used for the primary analysis (Section 4.2.1.4), including a factor for the relevant subgroup and the treatment-by-subgroup interaction, will be used for each subgroup analysis. HR for each level of the subgroup will be estimated separately.

The presentation of the results will include the estimate of the HR between treatment arms in the respective sub-group, the corresponding 95% CI and the p-value for the interaction term.

Results will also be plotted using a forest plot.

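### Adding AF history, prior stroke/TIA and age to the primary Cox model would be a cheap efficiency gain; the region-only model is valid but leaves it unused

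*SAP*

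**What the plan says.** Protocol 9.4.2.1 names treatment arm and geographic region as covariates and then leaves the door open: "Other covariates may also be included as appropriate; further details of the statistical model will be specified in the SAP". SAP 4.2.1.4 settles the matter with a "Cox regression model that includes the following factors/covariates: treatment group, geographic region" and adds nothing further.

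The candidate covariates are in hand. Age is recorded as a continuous demographic variable (SAP 4.1.4.1), and medical history is taken at Visit 1 (Protocol Table 1). SAP 4.2.1.7 lists age, prior stroke/TIA and prior AF, the last as "Atrial Fibrillation (Yes, No", among its baseline and prognostic factors, but only to examine consistency of effect. Neither the sensitivity analyses in SAP 4.2.1.5 nor the supplementary analyses in 4.2.1.6 include a covariate-adjusted overall estimate. Randomization is stratified by country only (Protocol 6.3).

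The design assumption is "Assuming the true HR for SZC versus placebo is 0.8", under which "730 primary endpoint events will result in 84.7% statistical power" (SAP 3.3). SAP 3.3 does not say whether that 0.8 is conditional on anything beyond the model to be fitted.

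**The concern.** AF admissions and stroke are both components of the primary endpoint. Protocol 2.2 describes AF as among the strongest risk factors for ischemic stroke and adds: "The estimated prevalence of AF among patients with ESRD in observational studies has been reported to be as high as 27" (per cent). Only AF needing immediate or urgent intervention is an exclusion (Protocol 5.2), so participants with an AF history can enter. It would be surprising if AF history, prior stroke/TIA and age did not predict the composite.

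The Cox hazard ratio is not collapsible. When the treatment works, omitting a prognostic factor moves the estimated hazard ratio toward 1, and the standard error at a fixed event count hardly falls to compensate. The test statistic therefore shrinks. Events are the scarce resource here: the SAP amendment history records a larger sample to speed accrual and a smaller event target to shorten the trial. The primary test also gates the whole secondary hierarchy (SAP 4.2.3), so even a small gain from data already collected is worth having.

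**Working it through.** **1. Reproduce the stated power.** Inputs from SAP 3.1 and 3.3: hazard ratio 0.8, 730 events, 1:1 allocation, efficacy look at 511 events (511/730 = 0.70), two-sided levels 1.64% and 4.46%.

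Drift at the final look: θ = |ln 0.8| × √730 / 2 = 0.22314 × 13.509 = 3.0145.

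Critical values are 2.400 at the interim and 2.009 at the final. The two statistics have means θ√0.70 = 2.522 and θ = 3.0145, and correlation √0.70. The probability of crossing at either look is 84.8%, against 84.7% stated. The final look alone gives 84.3%. The plan's figure is reproduced.

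**2. Fit both models to the same simulated trials.** There were 1,500 trials per scenario, with 2,800 participants, 32-month uniform accrual, a placebo rate of 0.11 per patient-year, a cut at 730 events and a true hazard ratio of 0.80 conditional on the covariates. Each data set was fitted with treatment + region, and again with AF history, prior stroke/TIA and age added. The mean Wald Z went through the boundary in step 1.

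These inputs are assumptions that the documents do not give: the covariate hazard ratios, prior stroke/TIA prevalence of 10–15%, age SD of 13 years, no region effect, and competing death of 0 or 0.12 per year. AF prevalence is 27% unless marked; that figure comes from the protocol's background literature, not from enrolled participants.

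Ranges in the table span the two death rates. Hazard ratios are for AF history / stroke or TIA / age per decade.

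| Assumed prognosis | Mean Z, region-only → adjusted | Power if 0.80 is conditional, region-only → adjusted | Adjusted power if 0.80 is the region-only HR |
|---|---|---|---|
| Near-null: 1.3 / 1.2 / 1.05, AF 15% | 2.988–3.002 → 2.998–3.015 | 84.2–84.5% → 84.4–84.8% | 85.0–85.1% |
| Weak: 1.5 / 1.3 / 1.10 | 2.964–2.966 → 3.001–3.009 | 83.6% → 84.5–84.7% | 85.7–85.8% |
| Moderate, AF 15%: 2.0 / 1.5 / 1.20 | 2.890–2.897 → 3.002–3.009 | 81.7–81.9% → 84.5–84.7% | 87.2–87.5% |
| Moderate: 2.0 / 1.5 / 1.20 | 2.860–2.878 → 3.001–3.003 | 80.9–81.4% → 84.5% | 87.7–88.0% |
| Strong: 3.0 / 2.0 / 1.30 | 2.640–2.686 → 2.982–2.997 | 74.4–75.8% → 84.0–84.4% | 91.5–92.2% |

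The last column multiplies the design drift by the ratio of the two Z values. In the weak case without competing death, for example, 3.0145 × 3.001/2.964 = 3.052, which gives 85.7%.

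Within scenarios the gains are about 0.3 (near-null), 0.9–1.0 (weak), 2.6–3.0 (moderate, AF 15%), 3.1–3.6 (moderate) and 8.6–9.6 points (strong). The region-only estimate moves from 0.80 to about 0.802 (weak) or 0.807–0.808 (moderate). The simulation error of the paired Z difference is about 0.004 (weak) and 0.008 (moderate), well below the differences of 0.037 to 0.141.

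**3. Cross-check.** A separate large-sample simulation with AF at 27% and 21–53 months of follow-up gave, against 84.8% adjusted: 83.9% region-only for AF hazard ratio 2 alone; 81.5% for AF hazard ratio 3 alone; and about 81–82% for AF 2.5, stroke 1.5 and age 1.3 per SD.

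**4. Express the gain in events.** Events needed scale with the squared Z ratio. Weak, without competing death: 730 × (3.001/2.964)² = 748, about 18 more. Moderate, with competing death: 730 × (3.001/2.860)² = 804, about 74 more.

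**The case against.** The strongest reply is that nothing here is wrong. The protocol made further covariates optional and left the choice to the SAP. The SAP pre-specified a simple model that is consistent with the protocol and controls type I error, since under the null both models target a hazard ratio of 1. All of that stands.

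A reader might infer that the trial falls 1 to 4 points short of its stated power. The documents do not support that. If 0.80 is the hazard ratio that the region-only model estimates, which is a natural reading of a design that fits that model, 84.7% is right and the points are a gain not taken. A shortfall exists only if 0.80 is read as conditional on AF, stroke/TIA and age, which neither document says.

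A reader might also infer that every secondary Cox test is weakened because SAP 4.2.2.1 reuses the primary model. That is not shown. Nothing in the documents makes AF history or prior stroke prognostic for time to rescue therapy, and no secondary endpoint was simulated.

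Nor is the simple model without merit. Region comes from the country recorded in the randomization system, whereas investigator-recorded history may be missing or unevenly ascertained. Without a rule for missing values, a default complete-case fit could drop randomized participants or events from the full analysis set. The adjusted hazard ratio is also conditional on more factors. These are reasons to specify the adjustment carefully; they do not remove the gain.

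The subgroup models in SAP 4.2.1.7 do contain these factors, but with treatment interactions, one factor at a time. They give no adjusted overall effect.

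**Conclusion.** This is an efficiency improvement, not an error. The omission, the availability of the covariates and the direction of the effect are firm. The size is conditional, because the documents give neither the covariates' hazard ratios on the composite nor the prevalence of prior stroke/TIA, and 27% is an upper literature figure for AF. Exclusions such as pacemakers, defibrillators and AF needing urgent intervention leave the enrolled prevalence uncertain.

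Across the weak and moderate scenarios and the cross-check cases, which use AF hazard ratios from 1.5 to 3, the gain is roughly 1 to 4 points of power at 730 events. It is near zero if the factors barely predict, and approaches 10 points if all three predict strongly. In no scenario did adjustment reduce power. The change is worth making, but the trial's conclusions would remain valid without it.

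**What to change.** Before any unblinded efficacy look, amend SAP 4.2.1.4 so that the primary Cox model contains treatment, region, history of AF (yes/no), prior stroke/TIA (yes/no) and age (continuous).

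- State a simple missing-covariate rule so that no randomized participant leaves the full analysis set; for example, no recorded history counts as no.
- Use the same model at the 511-event interim and at the final analysis, and name it in the DMC charter.
- Keep the region-only model as a sensitivity analysis.
- Extending the adjustment to the arrhythmia, SCD, stroke and death endpoints is reasonable. For time to rescue therapy there is no demonstrated gain.

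Adding the adjusted model only as a supplementary analysis would speak to robustness but would not raise the power of the primary test.

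The cost is wording in the SAP and DMC charter, with no new data collection. The one small downside is that the reported hazard ratio becomes conditional on three more baseline factors, as it already is on region.

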##### Normokalemia

Two definitions of normokalemic will be used to assess the likelihood of a patient being normokalemic at the 12 months visit. For the purpose of analyzing the corresponding secondary objective, normokalemia will be defined as:

- S-K of 4.0-5.5 mmol/L (yes/no), as measured by the central lab, after the long interdialytic interval (LIDI).

For the purpose of analyzing the corresponding exploratory objective, normokalemia will be defined as:

- S-K of 4.0-5.0 mmol/L (yes/no), as measured by the central lab, after the long interdialytic interval (LIDI).

A logistic regression model with the binary variable (yes/no) as response and the same covariates as for the main analysis of the primary objective described in Section 4.2.1.4 will be used. The estimated odds ratio, corresponding 95% confidence interval, and two-sided p-value will be presented. The proportion of normokalemic subjects in each treatment arm

will also be presented, with the number of patients with available SK data in the respective treatment arms used as the denominator.

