#### **4.2.3 Multiplicity/Multiple Comparisons**

Testing for efficacy will be performed at two time points, first at 0.7 information fraction and at the final analysis. The significance levels for the interim and the final analyses will be adjusted to control the overall type I error rate at two-sided 5%. At the efficacy interim analysis, the hypothesis for the primary endpoint will be tested at two-sided 1.64% significance level (O'Brian and Fleming method implemented by East 6.5, Copyright © 2018 Cytel Inc.). If the outcome of the interim analysis is to stop the trial for efficacy, then the interim analysis results will be considered as the primary efficacy results. However, a supplementary analysis will be performed with the additional data up to the study termination.

If the trial does not stop at any interim, then the final analysis planned at 730 adjudicated events, will be performed at a two-sided significance level of 4.46%. If the actual information fraction at the efficacy interim look deviates from 0.70, the significance level

for the final analysis will be adjusted based on the actual number of adjudicated primary events at the interim and final analyses.

To control the familywise Type I error rate, a fixed sequence multiple testing procedure for primary and secondary endpoints will be performed.

For the primary endpoint, the following hypothesis will be tested:

$H_0: HR[\text{SZC:placebo}] = 1$

Versus

$H_1: HR[\text{SZC:placebo}] \neq 1$

If study is terminated early prior to conducting efficacy and futility interim analyses and for reasons unrelated to efficacy, primary endpoint will be tested at 5% two-sided significance level.

Once the null hypothesis concerning the primary efficacy endpoint is rejected, the hypotheses for the secondary efficacy endpoints will be tested separately in the order listed in Table 2, with the same alpha level as the primary endpoint. The testing procedure will continue down the hierarchy if the current endpoint is rejected and will stop if the current endpoint is not rejected.

No multiplicity correction will be applied to the family of exploratory analyses. Hence, the results obtained from these should be regarded as hypothesis generating, rather than confirmatory.

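### Tests run at 4.46% (final) or 1.64% (interim) but intervals are nominal 95%, so a reported interval can disagree with its test, and an early-stop interval can under-cover if the effect is weaker than planned

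*SAP*

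**What the plan says.** SAP 4.2.3 sets the levels so that they are "adjusted to control the overall type I error rate at two-sided 5" per cent. At the efficacy interim "the hypothesis for the primary endpoint will be tested at two-sided 1.64% significance level". If the trial continues, the final analysis "will be performed at a two-sided significance level of 4.46" per cent, recalculated if the interim does not fall at an information fraction of 0.70. The secondary endpoints are tested in fixed sequence at the alpha used for the primary.

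The intervals do not follow these levels. For the primary endpoint SAP 4.2.1.4 reports "the corresponding 95% two-sided confidence interval (CI) as well as the two-sided p-value". For the binary potassium endpoints SAP 4.2.2 says "The estimated odds ratio, corresponding 95% confidence interval, and two-sided p-value will be presented". SAP 4.2.2.2 uses 95% for the event counts, the time-to-event secondaries repeat the primary analysis (SAP 4.2.2.1), and protocol 9.4.2 uses 95% throughout.

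SAP 4.2.1.4 bases rejection on the p-value against the limit in SAP 4.2.3. If the trial stops for efficacy at the interim, "then the interim analysis results will be considered as the primary efficacy results", with a supplementary analysis adding the data up to study termination. Neither document gives an interval matched to the test level, or a rule for reading a 95% interval that disagrees with its test.

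**The concern.** A test at level alpha and an interval at 1 minus alpha give the same answer. A test at 4.46% beside a 95% interval need not. A borderline final result could therefore show an interval excluding HR 1 next to a failed primary and a stopped hierarchy, with no prespecified way to read it.

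An early stop raises a second matter. Stopping selects favourable estimates, and the fixed-sample interim interval then becomes the result of record. Under the sponsor's own assumption (HR 0.80) such a stop is slightly more likely than not. The tested secondaries would then carry 1.64% as their alpha while their intervals stay at 95%, so for them the zone of disagreement is p from 0.0164 to 0.05.

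**Working it through.** **Inputs.** Interim 511 events and final 730 events (SAP 3.1); levels 1.64% and 4.46% (SAP 4.2.3); HR 0.80 and 1:1 allocation (SAP 3.3). Assumptions: SE(log HR) = 2/√events, exactly 511 and 730 events, and non-binding futility not applied.

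**Reproducing the plan.** A classical O'Brien-Fleming boundary with final critical value c and interim value c/√0.70, solved for overall two-sided 5%, gives c = 2.008. The levels are then 1.64% and 4.46%, as stated. The two stated levels together spend 4.996%. With HR 0.80 the two-look power is 84.8%; SAP 3.3 says "730 primary endpoint events will result in 84.7% statistical power". The design is reproduced.

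**Final analysis.** Critical values are z = 2.008 (4.46%) and 1.960 (5%), and SE = 2/√730 = 0.0740.
- Null rejected when HR ≤ exp(−2.008 × 0.0740) = 0.862.
- 95% interval excludes 1 when HR ≤ exp(−1.960 × 0.0740) = 0.865.
- Example: HR 0.8633 has 95% interval 0.747 to 0.998 but 95.54% interval 0.744 to 1.002.

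The probability of reaching the final analysis and landing in this zone (simulation, 3 to 4 million trials per true HR) is 0.5% at HR 1, 1.5% at 0.90, about 1.8% at 0.86, 1.7% at 0.85 and 1.0% at 0.80. At HR 1 the reported 95% interval excludes 1 in about 4.996% + 0.49% ≈ 5.5% of trials, so coverage is 94.5%.

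**Efficacy stop at 511 events.** SE = 2/√511 = 0.0885, and the boundary HR is exp(−2.400 × 0.0885) = 0.809. Let m = ln(HR)/SE and a = −2.400 − m. The stopping probability is Φ(a), and the mean z given a stop is m − φ(a)/Φ(a).
- HR 0.80: m = −2.522, a = 0.122, Φ(a) = 0.549.
- Mean z given a stop = −2.522 − 0.396/0.549 = −3.244.
- Geometric mean HR = exp(−3.244 × 0.0885) = 0.75.

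For true HRs from 0.80 to 0.90, every miss after a stop lies on the side that overstates benefit. Coverage given a stop is therefore (Φ(a) − tail)/Φ(a), with tail 0.025 for the 95% interval and 0.0082 for the 98.36% interval.

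| True HR | P(stop) | Mean HR given stop | 95% coverage given stop | 98.36% coverage given stop |
|---|---|---|---|---|
| 0.80 | 55% | 0.75 | 95% | 98.5% |
| 0.85 | 29% | 0.765 | 91% | 97% |
| 0.90 | 11% | 0.775 | 78% | 93% |

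**All trials together.** Coverage of the 95% interval is 94.5% at HR 1, 94.7% at 0.90 and 95.0% at both 0.85 and 0.80. The mean HR at true HR 0.80 is 0.792.

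**Secondaries after an interim stop.** The documents give no expected test statistic for these, so it is assumed here. Ignoring correlation with the primary, the chance of a p-value between 0.0164 and 0.05 is 3% if the expected z is 0, 9% at 1, 17% at 2.2 and 13% at 3.

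**The case against.** The strongest reply is that the plan makes no inferential error. The p-value decides, the interval is never a decision criterion, and the two levels spend just under 5%. A reader might infer from the mismatch that type I error is inflated; the documents do not support that. Nominal 95% intervals beside an adjusted alpha can also be defended as a reporting convention, used alike in both documents.

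The final-analysis zone is also small: 0.003 on the HR scale. If the futility rule is followed, its probability under the null halves to about 0.25%. For the primary endpoint the interim zone matters little, because the trial continues when the boundary is not crossed.

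A reader might also conclude that early-stop results are badly misleading in general. That goes too far. At the design HR, coverage given a stop is 95% (though all misses fall on one side), overall coverage is near nominal, and the planned supplementary analysis reports the later data. Under-coverage after a stop matters when the true effect is weaker than 0.80.

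A stage-wise adjusted interval with a median-unbiased HR may look like the natural remedy. It would do nothing here. The stop occurs at the first and only efficacy look, where those quantities equal the unadjusted ones: HR 0.78 at 511 events gives 0.656 to 0.928 either way.

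Finally, not every interval is mismatched. If the study ends before any interim for reasons unrelated to efficacy, SAP 4.2.3 tests at 5% and the 95% interval fits. Nor can level-matching make a fixed sequence fully coherent: once one endpoint fails, a later interval can still exclude the null without a rejection.

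All of this stands and limits the size of the point. It does not remove the mismatch or supply a reading rule.

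**Conclusion.** The concern holds as a reporting mismatch, not as a failure of error control. At the final analysis it affects at most about 1.8% of trials over the HRs examined and costs about half a percentage point of coverage at HR 1. After an efficacy stop it matters more: the primary interval covers 91% at true HR 0.85 and 78% at 0.90, and the tested secondaries have a wide zone in which test and interval disagree. The figures rest on the assumptions listed with the inputs. The change is worth making because it is nearly free, and because an interval level chosen after seeing a borderline result would not be credible.

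**What to change.** In SAP 4.2.1.4, 4.2.2 and 4.2.3, state that the primary endpoint and each formally tested secondary endpoint are reported with an interval at 1 minus the applied alpha:
- 95.54% at the final analysis, or 1 minus the level recalculated for the actual information fraction;
- 98.36% if the trial stops at the efficacy interim;
- 95% if the 5% early-termination rule applies.

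Label any additional nominal 95% interval descriptive, and likewise intervals for endpoints that come after the hierarchy has stopped. Align protocol 9.4.2 at the next amendment. Do not add a stage-wise interval or a median-unbiased HR.

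The cost is SAP and table-shell wording. On the log scale the final interval widens by about 2.5% (2.008/1.960), and an interim-stop interval by about 22% (2.400/1.960). In return, coverage at HR 1 returns to 95.0%, and coverage after a stop rises to 97% at HR 0.85 and 93% at 0.90. The change does not remove the early-stop bias in the HR point estimate, so the report should say so and show the supplementary analysis to study termination beside the interim result.
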